14 SAFETY ANALYSES

The safety analysis will be performed on the Safety Analysis Set using descriptive statistics. No formal statistical testing will be performed for any of the safety endpoints.

14.1 Adverse Events

All adverse events (AEs) will be coded using MedDRA version 24.0 or higher.

An AE (classified by preferred term) will be considered a treatment-emergent AE (TEAE) if it starts after the first study dose administration and no later than last study dose date + 30 days. AEs reported on Day 1 based on Baseline (pre-dose) findings (e.g. clinically significantly abnormal vital signs, laboratory test results, or electrocardiogram parameters) will not be considered as TEAEs.

The event counts and the number and percentage of subjects reporting TEAEs will be tabulated by SOC and preferred term; and, by SOC, preferred term, and maximum severity. If more than one AE occurs with the same preferred term for the same subject, the subject will be counted only once for that preferred term using the most severe and more related occurrence for the summarization by severity and by relationship to study drug, respectively.

The event counts and the number and percentage of subjects with any TEAEs will also be tabulated by preferred term without SOCs.

The incidence of most frequently reported (preferred terms reported by $\geq 5\%$ of subjects) TEAEs, TEAEs leading to discontinuation, TEAEs related to study drug, TEAEs by maximum severity, fatal TEAEs (i.e., events that cause death), serious TEAEs, and serious TEAEs related to study drug, will be summarized by SOC and preferred term.

The relationship of selected AEs to COVID-19 will be assessed as detailed in the GSD and provided in a listing.

An AE listing by subject will display all events, including those which are not treatment-emergent, and will include the verbatim term in addition to the MedDRA SOC and preferred term. Separate listings will be provided for TEAEs leading to discontinuation, TEAEs related to study drug, SAEs and fatal AEs.

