### **5.1.3 Dosing and Administration**

At the Baseline visit of Study ACP-103-070, study drug will be dispensed to the subject to take home. The subject and their parent/LAR will be provided instructions for the subject's first dose of study drug on the day after the Baseline visit.

Each daily dose consists of one capsule. Subjects should be instructed to take one capsule, orally, once daily, in the morning, at the same time every day. Subjects should be instructed to not to open the capsules. The capsules may be taken with or without food.

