#### **7.2.3 Duration**

The start and stop dates for AEs will be recorded using the following criteria:

- **Start:** Date of the first episode of the AE or date of worsening in severity
- **Stop:** Date when AE recovered or resolved, recovered or resolved with sequelae, or worsened in severity

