## 7.3 Time Period and Frequency for Event Assessment and Follow-up

Adverse events will be recorded from the first dose of open-label study drug through the study safety follow-up period. All ongoing AEs from the antecedent double-blind study will be carried over and recorded from Baseline for the ACP-103-070 study until resolution or the follow-up safety assessment. If an AE is ongoing at the end of the study safety follow-up period, every reasonable attempt should be made to follow and appropriately treat the subject until the AE resolves or until the Investigator deems the AE to be chronic or stable.

In the event that a subject discontinues from the study and has an ongoing AE at the time of discontinuation ([Section 4.5.1](#)), the subject should be followed and appropriately treated until the AE resolves or until the Investigator deems the AE to be chronic or stable. If a subject withdraws from the study because of an AE, no additional assessments may be performed ([Section 4.4](#)).

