### **9.5.1 Primary Analyses**

The primary endpoints for this study are TEAEs. All adverse events will be classified into standard terminology using the Medical Dictionary for Regulatory Activities (MedDRA). A TEAE is defined as an AE that started after first study dose administration and no later than last study dose date +30 days. The number and frequency of TEAEs will be summarized by system organ class and preferred term. TEAEs leading to discontinuation, TEAEs related to study drug, TEAEs by maximum severity, fatal TEAEs, serious TEAEs, and serious TEAEs related to study drug will also be summarized.

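### An adverse event ongoing at rollover that does not worsen, yet ends open-label treatment, is absent from the table and listing of TEAEs leading to discontinuation

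*SAP*

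**What the plan says.** The two documents define a TEAE in the same way. Protocol 9.5.1: "A TEAE is defined as an AE that started after first study dose administration and no later than last study dose date +30 days". SAP 14.1 says an event qualifies "if it starts after the first study dose administration and no later than last study dose date + 30 days". Neither definition contains a clause for pre-existing events that worsen.

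Protocol 7.3 brings unresolved events across from the double-blind study: "All ongoing AEs from the antecedent double-blind study will be carried over and recorded from Baseline for the ACP-103-070 study until resolution". Protocol 5.1.3 places the "first dose of study drug on the day after the Baseline visit".

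Protocol 7.2.3 sets the dating convention. The start of an event is the "Date of the first episode of the AE or date of worsening in severity", and its stop is the "Date when AE recovered or resolved, recovered or resolved with sequelae, or worsened in severity".

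On reporting, SAP 14.1 restricts the SOC and preferred-term summary of AE-driven stopping to TEAEs. For listings it states: "Separate listings will be provided for TEAEs leading to discontinuation, TEAEs related to study drug, SAEs and fatal AEs". It also provides a by-subject listing of every AE, treatment-emergent or not. SAP 6 tabulates discontinuations by primary reason and lists the reasons, with no condition on when an event began. Adverse event is one of the reasons named in Protocol 4.5.

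**The concern.** In a rollover study, a definition based only on onset can separate an event from its consequence. Suppose a child develops moderate somnolence in the double-blind study and completes that study. The somnolence persists unchanged, and open-label drug is stopped because of it at Week 6. The event did not end treatment in the antecedent study, because completing its treatment period is an entry criterion here (Protocol 4.1). In this study it began too early to be a TEAE. The plan therefore has no summary table that names it as the event that ended treatment.

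The primary objective is long-term safety and tolerability, and stopping drug because of an adverse event bears directly on that. For subjects already on pimavanserin, SAP 10.1.2 adds double-blind and open-label exposure together. The exposure crosses the study boundary, but the event that ends it does not. Because the rule only removes subjects from the AE-discontinuation table, any error in that table as a count of AE-driven stopping is downward.

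**Working it through.** **The plan's own figure.** The only design figure is the Rule of Three bound in Protocol 9.3 and SAP 3.5. With N = 193, 3/193 = 1.55%, which rounds to the stated 1.6%. The exact one-sided 95% bound is 1 − 0.05^(1/193) = 1.54%. The figure reproduces. The present point does not depend on it and takes only N = 193 from it.

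**Classification.** Let the Baseline visit be day B, so the first open-label dose is on day B + 1 (Protocol 5.1.3). A carried-over event may be entered with its antecedent start date or dated from Baseline. In both cases the start precedes the first dose. Applying Protocol 7.2.3 and SAP 14.1:

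| Event leading to stopping open-label drug | Start date used | TEAE? | In the TEAE-discontinuation table and listing? | Elsewhere |
|---|---|---|---|---|
| New after first dose | after first dose | yes | yes | disposition, all-AE listing |
| Carried over, worsens in severity on open-label drug | date of worsening | yes | yes | disposition, all-AE listing |
| Onset unclear relative to dosing (SAP 5.4.3) | treated as emergent | yes | yes | disposition, all-AE listing |
| Carried over, severity unchanged | on or before day B | **no** | **no** | disposition, all-AE listing |

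A disposition entry under adverse event depends on that being recorded as the primary reason. If another reason is recorded, such as withdrawal of consent by the parent, the last row appears only in the all-AE listing. Only the last row is lost from the table.

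**Serious events.** A carried-over event that becomes serious without a change in severity has the same start-date problem and drops out of the serious-TEAE summary. The SAE listing is not restricted to TEAEs, so the event is still listed. The documents do not say whether a change in seriousness alone opens a new record.

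**Size per subject.** Each omitted subject lowers the table by 1/193 = 0.52 percentage points. Two subjects are 1.04, three are 1.55 and five are 2.59.

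**Illustration on assumed rates.** The documents give neither r, the proportion stopping for an AE, nor s, the share of those stops caused by unworsened carried-over events. Both are assumptions here. The table would show r(1 − s), and the subjects missed number 193 × r × s.

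| r | s = 0 | s = 10% | s = 20% |
|---|---|---|---|
| 5% | 5.0% (0 missed) | 4.5% (1.0) | 4.0% (1.9) |
| 10% | 10.0% (0) | 9.0% (1.9) | 8.0% (3.9) |
| 15% | 15.0% (0) | 13.5% (2.9) | 12.0% (5.8) |

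For example, with r = 10% and s = 10%, 193 × 0.10 × 0.10 = 1.9 subjects are missed. The table then shows 9.0%, and disposition shows 10.0% if adverse event is the primary reason for all of them.

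**The case against.** The strongest reply is that the plan already reports AE-driven stopping without regard to onset, in the disposition table and the listing of reasons. A reader might infer from the TEAE rule that the study report as a whole would overstate tolerability. The documents do not support that: where adverse event is the primary reason, the subject is counted in disposition. What is missing is the preferred term in a summary, and any rule linking the two counts.

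A reader might also infer that every event beginning in the antecedent study is excluded. That is not so, because worsening in severity gives a new start date and makes the event a TEAE. SAP 14.1 does not repeat that convention, however, and depends on the protocol for it.

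Nor do the documents show that omissions would fall mainly on the subjects with the longest exposure. Prior-placebo subjects also carry events over, and a child stopping at Week 6 after 6 weeks of double-blind drug has about 12 weeks of exposure, far less than a 52-week completer. For prior-placebo subjects the event began before any pimavanserin, so leaving it out of a treatment-emergent table is correct. A summary regardless of onset must therefore separate the two groups.

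Eligibility also narrows the pool. Subjects must be clinically and medically stable in the investigator's opinion, and a change in medical status that raises risk is exclusionary (Protocol 4.1 and 4.2). Finally, the TEAE definition is prespecified and the SAP follows it, and table specifications are in a separate document not available here.

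These points narrow the concern and limit its likely size. They do not supply a table showing which events made children stop.

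**Conclusion.** The point holds in a limited form. An event that is ongoing at rollover, stays at the same severity and leads to stopping open-label drug is left out of both the SOC and preferred-term table and the listing of TEAEs leading to discontinuation. As a count of AE-driven stopping, that table can be too low but not too high through this mechanism, and it may not agree with disposition.

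The size cannot be determined from the documents and may be zero. The firm figure is 0.52 percentage points per omitted subject, if all 193 expected subjects enrol. The illustrative range of 0 to about 5.8 subjects rests entirely on assumed rates. The conclusion also assumes that sites apply the Protocol 7.2.3 dating rule as written. It is a reporting gap worth closing in a study whose primary objective is safety and tolerability. It is not evidence that the overall account of tolerability would be wrong.

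**What to change.** Amend SAP 14.1 as follows, leaving the TEAE definition unchanged.

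1. Add a summary by SOC and preferred term of AEs leading to discontinuation of open-label drug regardless of onset date. Key it on the action-taken category *Drug withdrawn* (Protocol 7.2.5). Show TEAEs as a subset, and split carried-over events by antecedent treatment (pimavanserin or placebo). Extend the matching listing in the same way.
2. State that a carried-over event that worsens in severity after the first open-label dose takes the date of worsening as its start and is a TEAE, citing Protocol 7.2.3.
3. Reconcile the new total with the disposition count for adverse event. Explain differences subject by subject, because the two can differ in either direction when the primary reason and the action taken do not match.
4. Add to the serious-AE summary the carried-over events that become serious on open-label drug, using the seriousness field (Protocol 7.2.8). The SAE listing already covers them.

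The cost is SAP wording and one or two extra tables from data already collected. The reported discontinuation rate may be slightly less favourable.

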## **2 STUDY OBJECTIVES AND ENDPOINTS**

### **2.1 Primary Objective**

- To evaluate the long-term safety and tolerability of pimavanserin after 52 weeks of treatment in children and adolescents with ASD

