2 OBJECTIVES

2.1 Primary Objective

To evaluate the long-term safety and tolerability of pimavanserin after 52 weeks of treatment in children and adolescents with autism spectrum disorder (ASD).

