4 ANALYSIS SETS

Safety Analysis Set

The Safety Analysis Set will include all subjects who received at least one dose of open-label study drug. The Safety Analysis Set will be used for all analyses.

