10.1.1 Exposure to Open-label Pimavanserin

For each subject, the duration of exposure to open-label pimavanserin (open-label last dose date – open-label first dose date + 1), cumulative dose (first multiply the number of doses taken by the dose level for each kit utilized during the open-label study period, then sum the results from

all kits), and average daily dose (cumulative dose in mg divided by duration of open-label exposure in days) will be calculated and summarized.

Duration of OL pimavanserin exposure will be summarized as both continuous and categorical variables. For categorical presentation, the number and percentage of subjects in each of the following categories will be presented: <2 weeks (1 to 13 days), 2 to <6 weeks (14 to 41 days), 6 to <12 weeks (42 to 83 days), 12 to <20 weeks (84 to 139 days), 20 to <28 weeks (140 to 195 days), 28 to <36 weeks (196 to 251 days), 36 to <44 weeks (252 to 307 days), 44 to <52 weeks (308 to 363 days), and \geq 52 weeks (364 days or longer). Kaplan-Meier curves of duration on study drug will also be presented. In addition, summaries of whether subjects had any dose change (yes vs. no), their highest dose level (20 mg or 34 mg), their lowest dose level (10 mg or 20 mg), and their last dose level (10 mg, 20 mg, or 34 mg) will also be provided.

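### The primary endpoint is summarised only as TEAE counts and crude percentages with no allowance for time at risk, so late-onset 52-week risk can be understated when subjects drop out

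*SAP*

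**What the plan says.** - **Objective.** Protocol 2.1: "To evaluate the long-term safety and tolerability of pimavanserin after 52 weeks of treatment in children and adolescents with ASD". SAP 2.1 repeats it.
- **Endpoint.** Protocol 9.5.1: "The primary endpoints for this study are TEAEs". The planned summary there is "The number and frequency of TEAEs will be summarized by system organ class and preferred term".
- **Estimator.** SAP 14.1: "The event counts and the number and percentage of subjects reporting TEAEs will be tabulated by SOC and preferred term". Further tables cover maximum severity, relatedness, seriousness, fatal events, discontinuation and preferred terms in at least 5% of subjects. All are counts and percentages.
- **Denominator.** SAP 4 defines the only analysis set as "all subjects who received at least one dose of open-label study drug".
- **Window.** A TEAE starts after the first dose and "no later than last study dose date + 30 days" (SAP 14.1), so the observation period ends at a different time for each subject.
- **Follow-up is expected to vary.** SAP 6 tabulates discontinuations by reason. SAP 10.1.1 sorts exposure into classes from under 2 weeks to 52 weeks or more, and adds that "Kaplan-Meier curves of duration on study drug will also be presented". None of this is carried into the TEAE tables.
- SAP 19 records no change from the protocol's analyses.

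**The concern.** A crude percentage gives the same weight in the denominator to a subject observed for four weeks as to one observed for the whole year. If many subjects leave, a low percentage may mean low risk or short observation, and the planned tables do not separate the two. The loss is greatest for events that appear late. Those are what a 52-week extension can show and the 6-week antecedent study cannot. Protocol 6.4 lists class effects for active monitoring, among them weight gain, hyperglycaemia and extrapyramidal symptoms, and for these the timing of onset is of interest. No test, error rate or sample size is at stake, because the study is descriptive. What is at stake is whether the primary summary can be read as a statement about one year of treatment.

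**Working it through.** **1. The plan's own figure.** Protocol 9.3 and SAP 3.5 give an upper bound of 1.6% for an adverse event not seen in 193 subjects. Rule of Three: 3/193 = 1.554%, which rounds to 1.6%. It reproduces, but it treats all 193 subjects as fully observed.

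**2. Inputs for the illustration.** From the documents: 52 weeks of treatment, a 30-day post-dose window, N = 193. Assumed: true 52-week risk R = 10%; exponential dropout independent of the event; retention of 85, 70, 60 or 50%. The only dropout rate stated for planning, 15%, is for the antecedent study. The 85% row has the same size but is not a documented rate for this extension.

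**3. Subject-years on drug.** With the year as time unit and c = −ln(retention), mean time on drug is (1 − e^(−c))/c.

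| Retention | c | Subject-years (193 × mean) | 3/subject-years, per 100 |
|---|---|---|---|
| 85% | 0.1625 | 178 | 1.68 |
| 70% | 0.3567 | 162 | 1.85 |
| 60% | 0.5108 | 151 | 1.99 |
| 50% | 0.6931 | 139 | 2.15 |

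**4. Expected crude percentage.** Let w = 30/364 = 0.0824. A subject is still under observation at time t with probability 1 if t ≤ w, and e^(−c(t−w)) otherwise. Only events up to Week 52 are counted.

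*Constant hazard*, h = −ln(0.9) = 0.1054:

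crude = (1 − e^(−hw)) + e^(−hw) × h/(h+c) × (1 − e^(−(h+c)(1−w)))

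At 70% retention: 0.0086 + 0.9914 × 0.2280 × 0.3455 = 0.0868.

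*Onset only in the second half-year*, h = 0.1054/0.5 = 0.2107:

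crude = h/(h+c) × e^(−c(0.5−w)) × (1 − e^(−0.5(h+c)))

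At 70%: 0.3714 × 0.8616 × 0.2470 = 0.0790. At 50%: 0.2331 × 0.7487 × 0.3636 = 0.0635 (0.06346 before rounding).

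*Onset only in the first 6 weeks*, h = 0.1054/(6/52) = 0.9131, stopping at last dose:

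crude = h/(h+c) × (1 − e^(−(h+c)×6/52))

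At 50%: 0.5685 × 0.1692 = 0.0962. Adding the 30-day window brings all four rows to 10.0%.

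| Retention | Constant hazard | Second half-year only | First 6 weeks only (no window) |
|---|---|---|---|
| 85% | 9.4% | 9.0% | 9.9% |
| 70% | 8.7% | 7.9% | 9.8% |
| 60% | 8.2% | 7.1% | 9.7% |
| 50% | 7.7% | 6.3% | 9.6% |

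The true value is 10% in every cell.

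**The case against.** **The crude percentage is a legitimate summary.** It estimates the share of treated subjects who have an event during the treatment they actually took plus 30 days. It falls short only for a different target: the risk had everyone stayed on drug for 52 weeks. The documents do not name that target. This stands. The complaint is that the crude figure appears alone under an objective worded in terms of 52 weeks.

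**The 30-day window offsets part of the loss.** If completers' events after Week 52 are also counted, the constant-hazard figures become 10.0, 9.2, 8.7 and 8.1% at 85, 70, 60 and 50% retention, so nothing is lost at 85%. That compares up to 52 weeks plus 30 days of observation with a 52-week risk. Against the risk over 52 weeks plus 30 days, the ratio of crude to true is 0.93, 0.86 and 0.75 at 85, 70 and 50%. The window softens the effect but does not remove it.

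**Counts, listings and exposure tables are also planned.** This is so, and a reader could work out an approximate overall event rate afterwards. The counts have no time denominator, and nothing of the kind is prespecified.

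**Person-time methods bring assumptions of their own.** A rate per 100 subject-years presumes a roughly constant hazard, and censoring at discontinuation presumes that leaving is unrelated to risk. Protocol 4.5 lists lack of efficacy, non-compliance and physician decision among the reasons for stopping, so independence is doubtful. This stands, and it shapes the fix.

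**Stronger readings to resist.** A reader might infer that the crude percentages necessarily understate risk. The documents do not support that: no retention rate is given, and early-onset events are barely affected. A reader might also want a Kaplan-Meier estimate for TEAEs leading to discontinuation. Each subject stops for an AE, stops for another reason, or completes. With other discontinuations as competing events, cumulative incidence at the end of treatment is therefore essentially the crude percentage. Finally, comparison with the 6-week antecedent study is not an argument here, because neither document plans a TEAE comparison.

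**Conclusion.** The omission is confirmed in both documents: TEAEs are reported as counts and crude percentages of all dosed subjects, with no allowance for time at risk. The summary can therefore understate the 52-week on-treatment risk if dropout is appreciable, mainly for late-onset events.

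For a true risk of 10%, the shortfall at 85 to 50% retention is 0.6 to 2.3 percentage points under a constant hazard and 1.0 to 3.7 points for second-half onset. It is at most 0.4 points for onset in the first 6 weeks. These sizes rest on assumed retention, independent exponential dropout and the assumed hazard shapes. The documents fix only the direction for a subject observed for less than the year, not the amount. No inferential result is affected, so this is a recommended addition to the SAP and not a flaw that invalidates the planned tables.

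**What to change.** Keep every planned count and percentage, and add to SAP 14.1:

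1. **Exposure-adjusted incidence**: subjects with a first event per 100 subject-years at risk, with time running from first open-label dose to first event and censored at last dose + 30 days or end of follow-up, whichever is earlier. Report it for any TEAE, serious TEAEs, preferred terms in at least 5% of subjects, and the actively monitored events in Protocol 6.4.
2. **Incidence by onset interval**, for example in the exposure classes of SAP 10.1.1, with the number of subjects still at risk in each interval as the denominator.
3. **Optionally**, a time-to-first-event estimate at Week 52 with a 95% CI for the actively monitored events, stating whether discontinuation is censored or treated as a competing event. The two answer different questions.

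TEAEs leading to discontinuation can stay as crude percentages.

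Cost: SAP wording and a few more tables. Dose dates and AE onset dates are already derived or imputed (SAP 5.4.1, 5.4.3 and 10.1.1), so no new data or protocol procedure is needed. The rate assumes a roughly constant hazard, which the onset-interval table lets the reader check. Neither addition removes possible dependence between leaving and risk, and the report should say so.

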## 6.4 Safety Assessments

As known potential class side effects of antipsychotics, the following adverse events will be actively monitored, including hyperglycemia, leucopenia/neutropenia/agranulocytosis, orthostatic hypotension/bradycardia/syncope, QTc prolongation, akathisia and other extrapyramidal symptoms, weight gain, and somnolence. Criteria for identifying potentially clinically important laboratory values, ECG values, and vital signs are presented in [Appendix C](#), [Appendix D](#), and [Appendix F](#), respectively; and criteria for identifying additional ECG measurements of potential clinical relevance for Medical Monitoring purposes are presented in [Appendix E](#).

Circumstances may arise (e.g., pandemic, natural disaster, political upheaval, or technical issues) when on-site assessments of safety measures may not be possible. In those cases, assessments may be performed at the subject's place of residence either in person or via video technology or telephone, where possible. If a subject is unable to come to the site for lab draws and the site is unable to travel to the subject's place of residence, the subject may visit a local lab to obtain all safety labs. The Investigator must contact the Medical Monitor for approval with the plan. Sites must keep a log to identify details of all visits that are administered remotely.

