9 MEDICAL HISTORY

Medical and surgical history data will be coded using Medical Dictionary for Regulatory activities (MedDRA) version 24.0 or higher. The subject incidence will be summarized for each system organ class (SOC) and preferred term by cohort and overall, for Safety Analysis Set. A subject will be counted only once per SOC or per preferred term for the summary.

A listing of the SOC, preferred term, body system, verbatim term for the medical history condition/event, start and stop dates (when available), and an indicator for whether or not the condition is ongoing will be provided.

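### The class effects that Protocol 6.4 names as groups, above all extrapyramidal symptoms and orthostatic hypotension, have no planned count of children with at least one such TEAE

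*SAP*

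**What the plan says.** Protocol 6.4 (Safety Assessments) opens with a list: "As known potential class side effects of antipsychotics, the following adverse events will be actively monitored". Some entries are single effects. Others are sets: the list ends with "akathisia and other extrapyramidal symptoms, weight gain, and somnolence", and earlier entries join orthostatic hypotension with bradycardia and syncope, and leucopenia with neutropenia and agranulocytosis.

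TEAEs are the primary endpoint (Protocol 2.1.1). Protocol 9.5.1 fixes the level of summary: "The number and frequency of TEAEs will be summarized by system organ class and preferred term". SAP 14.1 follows it: "The event counts and the number and percentage of subjects reporting TEAEs will be tabulated by SOC and preferred term". It then plans a second table: "The event counts and the number and percentage of subjects with any TEAEs will also be tabulated by preferred term without SOCs".

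The only counting rule for repeated TEAEs in a subject is that "the subject will be counted only once for that preferred term". The frequent-event summary is also defined by single terms: "The incidence of most frequently reported (preferred terms reported by" at least 5% of subjects).

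Neither document defines events of special interest, a standardised MedDRA query or any other grouping of terms. SAP 14.5.3 says that syncope and somnolence will be summarised as TEAEs, without saying which terms count as either.

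**The concern.** The study's main purpose is long-term safety, and Protocol 6.4 says in advance which adverse effects it is looking for. Where an effect is named as a set of events, a reader of the study report will want to know how many children had at least one of them. The planned summaries answer a different question: how many had each separate term, and how many had anything in an organ class. An organ class is not a class effect.

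Term rows cannot simply be added, because one child may appear in several of them. If terms are grouped only after the data have been seen, the reported incidence depends on which terms are chosen. In an open-label, single-arm study, no blinded control group limits that choice.

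**Working it through.** **Inputs.** Planned N = 193, which assumes that every eligible subject enrols (Protocol 9.3, SAP 3.5). The cut-off of 5% or more applies per preferred term (SAP 14.1). The documents give no event rates, no number of terms per effect and no overlap between terms, so these are assumed below and shown over a range.

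**The plan's own figure.** The Rule of Three gives 3/193 = 1.55%, which rounds to the stated upper limit of 1.6%. It reproduces and is not in dispute. It is the only numerical statement of safety precision in the plan.

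**Step 1: what 5% means.** 0.05 × 193 = 9.65, so a term needs 10 subjects (10/193 = 5.2%) to enter the frequent-event table. Nine subjects (9/193 = 4.7%) stay out.

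**Step 2: what term rows say about a group.** With k terms of 9 subjects each, the number of children with at least one event lies between 9 (full overlap) and 9k (no overlap).

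| Terms (k) | Lowest grouped incidence | Highest grouped incidence |
|---|---|---|
| 2 | 9/193 = 4.7% | 18/193 = 9.3% |
| 3 | 9/193 = 4.7% | 27/193 = 14.0% |
| 4 | 9/193 = 4.7% | 36/193 = 18.7% |
| 5 | 9/193 = 4.7% | 45/193 = 23.3% |

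In every row no term reaches the 5% table, and the term table alone cannot show where in the range the truth lies. Lower enrolment does not change the picture. At N = 150 a term needs 8 subjects, and three terms of 7 give 4.7% to 14.0%. At N = 100 a term needs 5 subjects, and three terms of 4 give 4.0% to 12.0%.

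**Step 3: how often the 5% table would miss a group.** Assume a true grouped incidence split equally over k terms, with one term per affected child. The figures come from a multinomial simulation with N = 193 and 200,000 draws.

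| True grouped incidence | No term reaches 5%: k = 2 | k = 3 | k = 4 | Grouped count reaches 5% |
|---|---|---|---|---|
| 8% | 56.5% | 89.7% | 97.7% | about 95% |
| 10% | 24.1% | 69.4% | 90.6% | over 99% |
| 12% | 6.8% | 41.9% | 75.4% | about 100% |
| 15% | 0.5% | 11.3% | 41.5% | about 100% |

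The one-term-per-child assumption is the least favourable case. With overlap, each term count rises towards the group count and misses become rarer.

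**Step 4: which named effects have a subject-level incidence from another source.**

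- Hyperglycemia: yes, from the glucose and HbA1c criteria in SAP Table 3.
- Leucopenia and neutropenia: yes, from the leukocyte and neutrophil criteria in Table 3.
- QTc prolongation: yes, from the QTcF categories in SAP 14.4 and Table 6.
- Weight gain: yes, from the 7% criterion in Table 5.
- Bradycardia: yes, from the pulse criterion in Table 5.
- Syncope and somnolence: in part. They are asked about at each visit (Protocol 6.4.5 and 6.4.6) and summarised as TEAEs (SAP 14.5.3), but related terms are not grouped.
- Extrapyramidal symptoms: no. SAP 14.6.2 summarises ESRS-A scores and changes only, with no count of affected children. The total is missing if any item is missing (SAP 5.2.9).
- Orthostatic hypotension: no. Standing pressure is taken only when symptoms are reported (Protocol 6.4.2), and Table 5 has no orthostatic criterion.

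**The case against.** Much of the case against stands. A reader might infer that none of the named effects gets an incidence. The documents do not support that: Step 4 shows that most have subject-level counts from laboratory, ECG, vital-sign or weight data, and syncope and somnolence are summarised as TEAEs. A reader might also infer that TEAEs are counted term by term and in no other way. Organ-class rows are planned as well, although SAP 14.1 states no once-per-class rule for TEAEs, whereas SAP 9 does for medical history ("A subject will be counted only once per SOC or per preferred term for the summary"). Nor is anything hidden. The 5% table is an extra highlight; the full TEAE tables have no cut-off, and the by-subject listing shows every event, so a grouped count could be built from it later.

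It is also fair that Protocol 6.4 concerns collection and goes on to refer to the criteria for clinically important values. It promises no grouped AE table, so the SAP does not contradict the protocol. The documents show no coding, so how many terms each effect would take is unknown. Finally, SAP 1 puts table specifications in a separate document that is not available here, and a grouping there cannot be ruled out.

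What these points do not remove is the gap for the effects named as sets that have no measured-data count. That part rests on the protocol's own wording, not on any assumption about the coding dictionary. A listing allows a grouped count, but only with a grouping chosen after the data are known. The definition of a case for a primary-endpoint summary belongs in the SAP, which Protocol 9.1 says will set out methods in detail and be approved before database lock.

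**Conclusion.** The point holds in a limited form. For extrapyramidal symptoms and orthostatic hypotension, no analysis described in the SAP gives the number of children with at least one event, and the planned term rows cannot supply it. For syncope and somnolence the gap is smaller: a TEAE incidence exists, but related terms are not brought together.

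The size depends on assumed rates. Three terms of 9 subjects leave the grouped incidence open between 4.7% and 14.0%. At a true 10%, split equally over two to four terms without overlap, the chance that none reaches the frequent-event table is 24% to 91%. These figures show what could happen and do not predict what will.

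This is a worthwhile and cheap improvement to a descriptive safety analysis. It is not an error in a stated figure, a conflict between protocol and SAP, or a loss of data.

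**What to change.** In SAP 14.1, before database lock, pre-specify a preferred-term list or a standardised MedDRA query for the Protocol 6.4 effects. At a minimum, cover extrapyramidal symptoms, orthostatic hypotension/syncope, and somnolence. For each group, tabulate the number and percentage of subjects with at least one TEAE, each subject counted once per group. Show any TEAE, serious TEAEs and TEAEs leading to discontinuation, and present every group regardless of the 5% cut-off. If the separate table specifications already contain such a grouping, refer to it in the SAP.

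The cost is one term list, which needs medical agreement before lock, and one or two extra tables. Data collection does not change.
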